## **3.2 Analyses**

### **3.2.1 Pass/Fail Criteria**

Not Applicable.

### **3.2.2 Hypotheses**

The hierarchical testing procedure below is introduced to guarantee that the probability of Type I error is < 5% for all confirmative statements. The order of the hierarchical testing procedure will be:

1. PTA 4 pre-operative unaided vs. 3 months post-surgery (Primary efficacy analysis)
2. Adaptive speech recognition in noise (50% performance), signal to noise ratio (SNR) pre-operative unaided vs. 3 months post-surgery
3. Speech in quiet at 65dB SPL pre-operative unaided vs. 3 months post-surgery
4. APHAB Global pre-operative unaided vs. 3 months post-surgery
5. Hearing attribute (HUI) pre-operative situation vs. 3 months post-surgery
6. Mean of the 12 items (Total score) in the SSQ pre-op unaided vs. 3 months post-surgery

If the first analysis is significant the probability mass 0.05 will go to the second analysis. If the second analysis is also significant the probability mass 0.05 will go to the third analysis and so on. When the first non-significant analysis is reached this and all analyses thereafter will be non-confirmative while the previous analyses will be confirmative. If the first analysis is non-significant no analysis will be confirmative. All testing will be Alpha level of 0.05 and two-sided test will be used and the analysis will be performed on the ITT.

### **3.2.3 Primary Hypotheses**

Group mean free-field PTA4 (average of 500, 1000, 2000, and 4000 Hz) with the Investigational device at the 3-month postoperative interval will be improved over that measured preoperatively in the unaided condition (baseline).

This endpoint is represented by the following hypotheses:

$$H_0: \mu_F - \alpha_0 = 0,$$

$$H_a: \mu_F - \alpha_0 \neq 0,$$

where:

$\alpha_0$  = baseline preoperative PTA4;

$\mu_F$  = mean follow-up PTA4 3 months postoperative.

Change in free-field threshold audiometry: PTA4 (mean of 500, 1000, 2000 and 4000Hz), from unaided versus Investigational device at 3 months post-surgery visit for the ITT population, using Fisher's two-sided non-parametric permutation test for paired observations to demonstrate an improvement in PTA4.

Alpha level of 0.05 and two sided test will be used and the analysis will be performed on the ITT population.

Group mean Adaptive speech recognition in noise (50% performance), speech to noise ratio (SNR) with the Investigational device at the 3-month postoperative interval will be improved over that measured preoperatively in the unaided condition.

This endpoint is represented by the following hypotheses:

$$H_0: \mu_F - \alpha_0 = 0,$$

$$H_a: \mu_F - \alpha_0 \neq 0,$$

where:

$\alpha_0$  = baseline preoperative Adaptive speech recognition in noise (50% performance), speech to noise ratio (SNR);

$\mu_F$  = mean follow-up Adaptive speech recognition in noise (50% performance), speech to noise ratio (SNR) 3 months postoperative.

Change in Adaptive speech recognition in noise (50% performance), from unaided versus Investigational device at 3 months post-surgery visit for the ITT population, using Fisher's two-sided non-parametric permutation test for paired observations to demonstrate an improvement in PTA4.

Alpha level of 0.05 and two sided test will be used and the analysis will be performed on the ITT population.

Both PTA4 and SNR must be significant at alpha 0.05 for the primary analysis to be considered as confirmative.

Missing data will be handled according to 3.4.1.

### **3.2.4 Secondary Hypotheses**

Group mean **Speech in quiet at 65dB** when using the Investigational device at 3 months postoperative compared to the unaided hearing using Fisher's two-sided non-parametric permutation test for paired observations.

This endpoint is represented by the following hypotheses:

$$H_0: \mu_F - \alpha_0 = 0,$$

$$H_a: \mu_F - \alpha_0 \neq 0,$$

where:

$\alpha_0$  = baseline preoperative word recognition score;

$\mu_F$  = mean follow-up word recognition score 3 months postoperative.

Group mean **Global score using the Abbreviated Profile of Hearing Aid Benefit (APHAB)** when using the Investigational device at 3 months post surgery compared to

unaided hearing, using Fisher's two-sided non-parametric permutation test for paired observations.

This endpoint is represented by the following hypotheses:

$$H_0: \mu_F - \alpha_0 = 0,$$

$$H_a: \mu_F - \alpha_0 \neq 0,$$

where:

$\alpha_0$  = baseline APHAB Global score;

$\mu_F$  = mean follow-up APHAB Global score 3 months postoperative.

Group mean **Hearing attribute (HUI)** when using the Investigational device at 3 months post surgery compared to the preoperative hearing situation, using Fisher's two-sided non-parametric permutation test for paired observations.

This endpoint is represented by the following hypotheses:

$$H_0: \mu_F - \alpha_0 = 0,$$

$$H_a: \mu_F - \alpha_0 \neq 0,$$

where:

$\alpha_0$  = baseline Hearing attribute (HUI);

$\mu_F$  = mean follow-up Hearing attribute (HUI) 3 months post-fitting.

Group mean **Total score using the Speech, Spatial and Qualities of Hearing Scale (SSQ)** when using the Investigational device at 3 months post surgery compared to the unaided hearing, using Fisher's two-sided non-parametric permutation test for paired observations.

This endpoint is represented by the following hypotheses:

$$H_0: \mu_F - \alpha_0 = 0,$$

$$H_a: \mu_F - \alpha_0 \neq 0,$$

where:

$\alpha_0$  = baseline SSQ Total score;

$\mu_F$  = mean follow-up SSQ Total score 2 months post-fitting.

Missing data will be handled according to 3.4.1.

All other secondary outcomes will not be formally hypothesis tested but summarized and p-values will be calculated.

In addition to comparing follow up data with unaided analyses will also be made with Baha Power sound processor on a Baha Softband (screening).

### **3.2.5 Additional statistical issues**

If any paired analysis of dichotomous and ordered categorical variables (i.e. if any continuous variables will be categorized) will be made the Sign test will be used.

The main efficacy analyses will be performed at 3 months after surgery on the ITT population and complementary efficacy analyses will be performed 6 months after surgery on the ITT population. In addition, all analyses will be made on the PP population. Sub analyses will also be performed on one group consisting of Mixed/conductive subjects and one consisting of SSD subjects.

Primary safety analysis will be performed at 3 months post-surgery.

### **3.3 Analysis Datasets**

The final definition of the analysis sets (ITT, PP and Safety) will be taken at the clean file meeting before database lock.

All efficacy analyses will be performed on both ITT and PP populations.

#### **3.3.1 Safety**

The Safety population/dataset consists of all surgically treated subjects.

#### **3.3.2 Intent-to-Treat**

The Intention-to-Treat population/dataset (ITT) will include all subjects who have undergone surgical intervention.

Missing data will be handled according to 3.4.1.

#### **3.3.3 Per Protocol dataset**

The Per Protocol population/dataset (PP) will include subjects that have completed the study according to the protocol. Subjects that were incorrectly included or were considered major protocol violators that affect the primary analysis should be removed from the PP population/dataset.

Missing data will be handled according to 3.4.1.

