7.2.5 Enrolment & Investigation Duration

The following subject status definitions apply:

Screened: A consented subject who is being assessed for eligibility according to the Screening requirements.

Screen Fail: A consented subject that has been determined to not meet all eligibility criteria for enrolment.

Enrolled: Subjects who have met all eligibility criteria and have received the implant.

If a subject discontinues his/her participation in the investigation, he/she will not be replaced if this discontinuation occurs after surgery is performed. If this discontinuation occurs before surgery the subject will be replaced in order to reach 30 evaluable subjects.

The enrolment period for the investigation is anticipated to be approximately 4 - 6 months from the time of first subject consent to enrolment of the last subject.

The expected duration of each subject's participation in the investigation, is 6 months from surgery.

The anticipated total duration of the clinical investigation is maximum 12 - 15 months.

Completion of investigation is defined as last subject last visit. In the event of an ongoing SADEs at the time of this last visit, the investigation completion will be extended for a further 30 days, or until resolution or stabilisation of the event, whichever comes first.

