9.5 Analysis Populations

The final definition of the analysis sets (ITT, PP and Safety) will be taken at the clean file meeting before database lock.

- The Intention-to-Treat population (ITT) will include all subjects who have undergone surgical intervention.
- The Per Protocol population (PP) will include subjects that have completed the study according to the protocol. Subjects that were incorrectly included or were considered major protocol violators that affect the primary analysis should be removed from the PP population.
- The Safety population consists of all surgically treated subjects

All efficacy analyses will be performed on both ITT and PP populations.

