14 DATA MANAGEMENT

The CRF will capture subject status according to the following criteria:

- Consented: Signed consent and eligibility evaluations underway

- Screen Fail: Subject determined not to be eligible to proceed for participation
- Enrolled: First use of the Investigational device following completion of screening activities and confirmation of eligibility
- Withdrawn: Enrolled subjects who withdraw or are withdrawn by the Investigator or Sponsor before the expected last visit.
- Complete: Enrolled subjects who complete the planned follow up visits according to this CIP.

Source data will be captured in clinic notes, paper-based source data worksheets, or printed directly from testing software. Before initiation of the clinical investigation the PI should together with the CRA complete the template “Origin of source data” stipulating where source data should be recorded at the investigation site. If electronic medical records do not permit read only access for monitoring purposes, a verified printout must be provided.

Data collection will be performed using [REDACTED] for electronic data capture (EDC) on electronic Case Report Forms (eCRFs). Site staff will be trained on the completion of the eCRFs prior to obtaining access to the system, and will have their own Login/Password. Access to clinical investigation information will be based on an individual’s role and responsibilities.

[REDACTED] uses role-based user permissions for data entry, viewing, and reporting options. All communications between users and the EDC server are encrypted. Web servers are protected by a managed firewall. This application is designed to be in compliance with applicable regulations including 21 CFR Part 11.

The application will include programmed data consistency checks and supports manual generation of data clarifications/queries, including documentation of site responses. The application maintains a comprehensive audit trail for all data entered, including updates and queries, and documents the time that each entry occurred and who made the entry.

Principal Investigators will affirm that the data for each subject at their site is accurate and complete by way of an electronic signature.

In addition, de-identified electronically generated data will be collected from the OFS. The unamended data file shall be regarded as the source.

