#### **3.5.1 Timing of analyses**

The first reporting of analyses will be made when all patients have completed their 3 months visit of the data up to 3 months. This analysis is regarded as the primary analysis. At the end of the study, at 6 months, the second and final reporting of the study will be made including all data up to the 6 months visit including data prior to the 3 months visit (ie all data in the study).

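### The per-protocol set requires 6-month completion although the primary report is at 3 months, and the interpolation rule does not exclude preoperative questionnaire scores as anchors

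*SAP*

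**What the plan says.** **PP set.** SAP 3.3.3 gives one definition: "The Per Protocol population/dataset (PP) will include subjects that have completed the study according to the protocol". Protocol 9.5 says the same. A further sentence in both removes wrongly included subjects and major violators whose violations bear on the primary analysis. Protocol 7.2.5 puts each subject's expected "participation in the investigation, is 6 months from surgery". The status list in Protocol 14 reads: "Complete: Enrolled subjects who complete the planned follow up visits according to this CIP". The last planned visit is at 6 months.

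**Timing.** SAP 3.5.1 says: "The first reporting of analyses will be made when all patients have completed their 3 months visit of the data up to 3 months". It adds: "This analysis is regarded as the primary analysis". A second, final report follows at 6 months and covers all study data, including those from before month 3. SAP 3.2.5, after placing the main analyses on ITT, says: "In addition, all analyses will be made on the PP population". SAP 3.3 leaves the final definition of the analysis sets to a clean file meeting ahead of database lock.

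**Imputation.** SAP 3.4.1 makes imputed data the main ITT analysis and non-imputed data a sensitivity analysis. Rule 1 carries the last observation forward. Rule 2 fills a gap that has recorded values on both sides: by interpolation for continuous variables, and by the previous visit's value for categorical ones. Rule 3 adds stochastic regression imputation as a sensitivity analysis. Baseline values may be neither imputed nor carried forward. The schedule (SAP 1.1) collects APHAB, SSQ and HUI only at baseline, 3 months and 6 months.

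**The concern.** The 3-month PP analysis is there to check the 3-month ITT result. If membership depends on reaching month 6, it depends instead on the date of surgery (first report) or on events after the endpoint was measured (final report). Neither says anything about the quality of the 3-month data.

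For the questionnaires, the only scheduled score before month 3 is preoperative: unaided for APHAB and SSQ, and the subject's current hearing situation for HUI. Interpolating from it would give a 3-month score that mixes a preoperative condition with an aided one. If the 3-month gain is already close to the 6-month gain, this understates it, and it does so in the main imputed analysis of the final report.

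**Working it through.** **The plan's own figure.** Inputs from SAP 3.1: n = 30, SNR change 7.6 dB (SD 8.1), PTA4 change 25 dB (SD 9.5), stated power 0.99 each. For a paired t-test at two-sided 0.05, the SNR noncentrality is 7.6/8.1 × √30 = 5.14, giving power 0.9987. For PTA4 it is 25/9.5 × √30 = 14.4, giving power above 0.9999. Both agree with the plan, and the sample size is not in dispute.

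**PP at the first report.** The documents do not give the share of subjects short of 6 months. As an illustration, assume surgeries spread evenly over E months, on-time visits, and a PP set fixed m months after the last 3-month visit. The share not yet at 6 months is then max(0, (3 − m)/E). For E = 4, 5, 6 (the planned enrolment period is 4 to 6 months):

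- m = 0: 75%, 60%, 50%
- m = 1: 50%, 40%, 33%
- m = 2: 25%, 20%, 17%
- m = 3: none, but by then the 6-month visits are done and the first report has lost its purpose.

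**PP at the final report.** Assume 1, 3 or 6 of 30 leave after a valid 3-month visit. The approximate 95% CI half-width for SNR change is t(0.975, n − 1) × 8.1/√n (the SAP plans bootstrap intervals):

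- n = 30: 3.02 dB
- n = 29: 3.08 dB
- n = 27: 3.20 dB
- n = 24: 3.42 dB

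SNR power at n = 24 is still 0.993. The loss is in what the PP analysis represents, and only slightly in precision.

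**Rule 2, first report.** With data cut at 3 months, a missing 3-month questionnaire score has only baseline before it. Carrying baseline forward is barred, so under rules 1 and 2 the score stays missing.

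**Rule 2, final report.** If the 6-month score exists, the gap lies between two recorded values. Put baseline at x weeks before surgery, month 3 at week 13 and month 6 at week 26. The weight on the 6-month score is w = (13 + x)/(26 + x). With baseline score B and the same gain G at 3 and 6 months, the filled score is (1 − w)B + w(B + G) = B + wG, so the filled change is wG. With k fills among 30, the mean gain becomes G[1 − (1 − w)k/30].

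- x = 0: w = 13/26 = 0.50; loss 1.7%, 5.0%, 10.0% for k = 1, 3, 6
- x = 8: w = 21/34 = 0.62; loss 1.3%, 3.8%, 7.6%

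The documents do not give the interval from baseline to surgery or the number of missing scores. The direction depends on equal gains: the filled value is unbiased if the true 3-month gain equals w times the 6-month gain.

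**The case against.** **On PP.** No sensible analyst would discard subjects from a report on data up to 3 months because month 6 lies ahead. The violator clause already refers to the primary analysis, and the clean file meeting can settle a 3-month rule. Protocol 14 lists CRF status labels that SAP 3.3.3 does not cite, and it defines enrolment differently from Protocol 7.2.5. A PP set of completers is also ordinary practice.

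Much of this stands. The meeting would probably prevent the worst outcome, and a completer set is reasonable for the 6-month analyses. But the violator clause only removes further subjects and does not waive completion. The 6-month duration follows from Protocol 7.2.5 and the schedule without section 14. The SAP describes one meeting and two reports, and writes no 3-month rule.

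A reader might infer that half to three quarters of subjects would be lost from PP at the first report. The documents do not support that. It needs even accrual and a set fixed on the day of the last 3-month visit, and the plan states neither.

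**On rule 2.** The bar on carrying baseline forward suggests that baseline was not meant to feed imputed values. If baseline counted as an anchor, the categorical half of rule 2 would carry it forward, against that bar. The non-imputed and stochastic regression analyses would help to show any distortion. This is the stronger objection: it makes the problem an unclosed gap in wording, not a stated intention. Still, the text does not exclude interpolation from baseline.

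A reader might also infer that the primary endpoints are exposed. PTA4, SNR and speech in quiet are measured with the device at fitting, so when that value is present a missing 3-month result is interpolated between two aided values.

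**Conclusion.** Both points hold as defects of wording with modest consequences. The PP definition does not fit a primary report at 3 months. At the first report the share affected is unknown. At the final report, 1 to 6 assumed late leavers widen the SNR half-width from 3.0 to 3.1-3.4 dB. Rule 2 leaves open a fill that would lower mean 3-month questionnaire gains by about 1.7%, 5% or 10% for 1, 3 or 6 fills of 30, with baseline at surgery and equal gains at 3 and 6 months.

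It would be wrong to conclude that the confirmatory claims are in doubt. All six steps of the hierarchy in SAP 3.2.2 are tested at 3 months on ITT, so PP membership does not enter. The first report is the designated primary analysis, and there the baseline interpolation cannot arise. The change is worth making because it is cheap; it is not a condition for the trial's validity.

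**What to change.** 1. In SAP 3.3.3, replace the single PP set with two. The 3-month set requires the 3-month visit and no major deviation up to 3 months affecting the 3-month endpoints; use it for all 3-month analyses in both reports. The 6-month set keeps the completion requirement and serves the 6-month analyses. Settle the 3-month set at a clean file meeting before the first report, and note the clarification against Protocol 9.5.
2. In SAP 3.4.1, state that rule 2 uses only post-operative aided values as anchors.

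The cost is a few lines of SAP text and one additional clean file meeting. No visit, sample size or confirmatory test changes. The downside of the second change is that some missing 3-month questionnaire scores stay missing under rules 1 and 2 in the final report, as they already would in the first.

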### **3.4 Additional Statistical Considerations**

#### **3.4.1 Missing, Unused or Spurious Data**

All ITT analyses will be performed/presented both for the imputed (main analyses) and for the non-imputed data (sensitivity analyses).

Imputation of missing values will be performed for all efficacy variables. No imputation of baseline values or baseline carry forward will be made. Imputations will be made according to the following rules:

1. If a value is missing at the end of a time period for a patient, last observation will be carried forward.
2. If a missing value is occurring between two time points with values, an interpolation will be made for continuous variables and for categorical variables the value from the previous visit will be carried forward.
3. As a sensitivity analysis imputation of missing values will be performed for all efficacy variables using stochastic regression imputations.

Spurious data will be cleaned prior to clean file meeting. If spurious data are detected after clean file is declared actions to consider will be;

1. unlock, correction of the spurious data and a new re-lock will be made alternatively,
2. a sensitivity analysis will be performed that accounts for the spurious data in a proper statistical fashion (e.g. non parametric methods).

### **3.4.2 Planned Interim Analysis**

No interim analyses are planned to be performed.

### **3.4.3 Criteria for Termination of the Clinical Investigation**

Not applicable.

### **3.4.4 Additional Statistical Analyses**

#### **3.4.4.1 Major protocol deviations**

Major protocol deviations are those that are considered to have an effect on the analysis. The number of patients with major protocol deviations will be summarised per treatment group. A list of protocol deviations will be produced.

#### **3.4.4.2 Demographics**

A descriptive presentation of demographic data will be presented as described in paragraph 3.7:

- Age collected as date of birth (month and year)
- Gender
- Race
- Tobacco use
  - Never /Current/Former
  - Primary method (Cigarettes/Cigars/Pipe/eCigarettes/Chewing/Other)
  - Cigarettes/day

#### **3.4.4.3 Medical history**

A descriptive presentation of medical history will be presented as described in paragraph 3.7:

- Relevant medical and surgical treatment during the past three years as judged by the investigator
- Current concomitant medication and treatments

#### **3.4.4.4 Hearing history**

Test ear (right/left)

A descriptive presentation of hearing history will be presented as described in paragraph 3.7:

- Type of hearing loss:
  - Conductive,
  - Mixed,
  - SSD
- Aetiology of hearing loss:

- (chronic) infection,
- tumour,
- trauma,
- malformation,
- otosclerosis,
- genetic
- unknown
- other
- History of hearing loss
  - progressive
  - progressive with sudden
  - sudden
  - congenital with progression (if age at onset was 0 month)
  - congenital without progression (if age at onset was 0 month)

### 3.4.4.5 Device history

#### Hearing aid

- Has the subject used hearing aid (never/current/former)
- Has the subject used hearing aid (never/current/former) on test side
- Has the subject used hearing aid (never/current/former) on non-test side
- Has the subject used hearing aid (never/current/former) on both test side and non-test side

